8.1.2.2 TMS MEASURES

We will determine **two TMS measures**: presence of **Motor Evoked Potential (MEP)** and amplitude of MEPs. These TMS measures support the exploratory aims/objectives outlined in section 3 above.

Presence or absence of Motor Evoked Potential (MEP): The resting motor threshold (rMT) is the lowest stimulus intensity of TMS that gives a recordable MEP from abductor pollicis brevis (50 μ V peak-to-peak). It is a measure of global motor system excitability at both cortex and spinal cord level. This parameter will be categorized into a binary variable (Present/1 or Absent/0) for the purpose of analysis. Present/1 means there is a recordable MEP, Absent/0 means there is no recordable MEP. Presence of MEP in a subject with a stroke typically suggests some degree of preservation of the corticospinal tract. It is possible that MEP is absent on the affected limb despite applying the stimulus on the lesional hemisphere if the CST is severely injured. rMT from non-paretic side is collected as well and serves as a reference to the paretic side. It is estimated that ~20% of patients may not have a recordable MEP from this study. If it turns out that only < 10% of patients do not have MEP and the number of subjects in the absent group is too small. We will use an alternative to analyze the data. We will use asymmetric index {i.e. (absolute value rMT on the affected side – absolute value of rMT on the unaffected side) / absolute value rMT on the affected side). If MEP is absent, a value of 100 % maximum stimulator output (MSO) will be assigned as rMT. If MEP is present, the rMT (% MSO required to produce 50 μ V peak-to-peak using PEST algorithm) will be compared between baseline and post-therapy sessions.

Size of the Motor Evoked Potential (MEP) The size of MEP (i.e. the peak to peak amplitude of a stable MEP that is ≥ 1 mV) provides an estimate of the extent of corticospinal tract and motor neuron activation by the magnetic stimulation. This is only done if the patient has a recordable MEP first. If patient does not have a recordable MEP, the amplitude of MEP will be set as 0. If the patient has a recordable MEP, the % MSO required to produce 1 mV peak-to-peak using PEST algorithm will be determined on baseline and post-therapy sessions. This value will be used as a testing stimulus (TS) in the paired-pulse stimulation (below) and therefore will be called as testing motor threshold (tMT). Patients with non-recordable 1 mV peak-to-peak MEP will be applied 100% MSO as TS in paired-pulse stimulation routine. 20 MEP at tMT with 4-7 seconds inter-pulse interval will be collected to determine the size of MEP. Comparison of MEP size will be performed between baseline and post-therapy sessions using baseline visit tMT to ensure that same stimulus intensity when comparing MEP size. The size of MEP from the non-paretic side will be collected as well and serves as a reference to the paretic side.

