3 OBJECTIVES AND ENDPOINTS

OBJECTIVES	ENDPOINTS	JUSTIFICATION FOR ENDPOINTS
------------	-----------	-----------------------------

Primary		
To determine whether there is an initial overall treatment effect among 3 dosing groups: • sham + mCIMT • 2 mA + mCIMT • 4 mA + mCIMT	FM-UE scale	FM-UE scale is the primary outcome and a measure of motor impairment
Efficacy is measured at day 15 after the initiation of the intervention.	WMFT time score	WMFT is a secondary outcome and a measure of functional motor activity
	SIS Hand Subscale	SIS Hand subscale is a secondary outcome and a measure of the quality of life
Secondary		
To confirm that the proposed intervention is safe, tolerable, and feasible to administer in a multi-site trial setting	Rate of adverse events	Safety needs to be monitored in a phase II study
	Visual Analog Scale	Visual Analog Scale measures tolerability
	Treatment completion rate	80% of treatment completion rate across sites without unexplained/unresolved variability is a measure of feasibility.
Tertiary/Exploratory		
To examine whether wCST-LL (structural assessment of integrity of descending motor tract) or MEPs (functional assessment of integrity of descending motor tract) or combination of both are correlated	wCST-LL (structural)	wCST-LL is a structural measure of integrity of descending motor tract using brain MRI that has shown promise in predicting motor outcomes.

with changes in FM-UE scale, and evaluate the utility of these measures as biomarkers for subject selection criteria in the future confirmatory Phase III study
	
MEPs (functional)
	
MEPs is a functional measure integrity of descending motor tract using TMS that has shown promise in predicting motor outcomes, but two of them have not been collected and compared in the same study.

To examine whether functional or structural changes in motor tracts correlate with changes in impairment and functional motor activity induced by the intervention.
	
Motor Evoked Potentials (MEPs) and Diffusion tensor imaging MRI.
	
MEPs can change in response to rehabilitation; Functional and structural aspects of motor tracts and the interaction between motor regions change after intervention. This change can be captured by comparing TMS and MRI measures before and after treatment

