8.1.2 EXPLORATORY AIMS MEASURES

8.1.2.1 IMAGING MEASURES

We will determine **two imaging measures**: weighted corticospinal tract lesion load (**wCST-LL**) that be derived from the pre-intervention MRI and the **fractional anisotropy (FA) measure** that will be derived from the pre- and post-intervention MRI. These imaging measures support the exploratory aims/objectives outlined in section 3 above.

wCST-LL: Three MRI sequences (T1-weighted, T2-weighted, and FLAIR imaging) will be used to define and quantify the stroke lesion. A 3D map of this lesion will be overlaid onto a canonical corticospinal tract which was derived from a group of elderly healthy control subjects and exists in our lab as a representative map of the CST; (see [name] et al., 2015 for details). The overlap area between the lesion and the canonical CST will constitute our measure of wCST-LL. The weighting of the lesion load is related to the probabilistic nature of the tract and its geometric changes while it traverses from the cortex through the internal capsule into the brainstem. The **wCST-LL** is a continuous measure expressed in cubic centimeter (cc) with 2 decimals.

Corticospinal Tract - fractional anisotropy values (CST-FA): FA values are derived from an MRI sequence called diffusion tensor imaging (DTI). FA values will be determined in maps of the CST. Canonical maps of the CST (stretching from the posterior limb of the internal capsules to the lower brainstem) exist in our laboratory and have been previously described (see Zheng and [name], 2015 for details). FA is a measure of tract integrity or how well fibers are aligned in one direction in a tract. Values are between 0-1. Fractional anisotropy values tell us something about the direction of water flow. If the value is closer to 1, water flows along major fiber tracts in one particular directions, which means that the fibers are healthy and well aligned. Typically, on the side of the stroke, we might see a decrease in FA or water not only flowing in one direction but multiple directions, reflecting a degeneration of a fibers in a tract as an effect of the stroke. FA values derived from a template of the CST on the lesional and contralesional hemisphere will be determined in the pre-intervention MRI and post-intervention MRI and changes in these FA values will be correlated with behavioral changes within the three treatment groups as specified in the SAP.

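### Resting motor threshold enters the biomarker aim only as MEP present or absent (about 80/20 expected); a graded threshold analysis should always be reported beside it

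*Combined protocol and SAP*

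**What the plan says.** Section 3 sets an exploratory aim: to see whether wCST-LL, MEPs or both correlate with FM-UE change, and whether they could serve to select Phase III patients. Part of its justification is that the "two of them have not been collected and compared in the same study".

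- **Threshold.** Section 8.1.2.2 obtains rMT in % MSO on both sides. For analysis, "This parameter will be categorized into a binary variable (Present/1 or Absent/0) for the purpose of analysis". On the expected split: "It is estimated that ~20% of patients may not have a recordable MEP from this study".
- **Fallback.** If fewer than 10% lack an MEP and that group is too small, the plan turns to a graded alternative: "We will use asymmetric index", built from affected-side and unaffected-side rMT. It also states: "If MEP is absent, a value of 100 % maximum stimulator output (MSO) will be assigned as rMT". A graded value is therefore available for every subject.
- **Second TMS measure.** The section names MEP presence "and amplitude of MEPs. These TMS measures support the exploratory aims/objectives outlined in section 3 above". Amplitude is set to 0 when no MEP can be recorded. Otherwise it is taken at the intensity that gives a 1 mV response.
- **Imaging marker.** Under section 8.1.2.1, wCST-LL "is a continuous measure expressed in cubic centimeter (cc) with 2 decimals".

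Sections 9.4 and 9.4.6 refer to the SAP for analysis details. The text available for this review contains no model relating the TMS and imaging markers to FM-UE change.

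**The concern.** At the expected split, about four subjects in five receive the same TMS score whether their threshold is near normal or close to the stimulator's limit. If motor gain falls steadily as the threshold rises, that information is measured and then set aside. To the extent that MEP presence is the TMS term compared with continuous wCST-LL, the comparison would understate a graded TMS signal.

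The switching rule adds a second difficulty. The form of the predictor depends on the observed share without an MEP. Just above 10% absent (13 of 129 subjects, about 4 per arm), the binary form still applies, and that is where it keeps least.

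At stake is what the trial can tell a Phase III team about patient selection.

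**Working it through.** **Inputs from the plan.** Total N = 129 (section 9.2); up to 15% lost, so 129 × 0.85 ≈ 110 evaluable; 20% without an MEP; switch below 10%. The plan gives no power, precision or effect size for the biomarker aim, so there is no biomarker figure to reproduce. The N does reproduce: 31/0.92² × 1.15 = 42.1, rounded up to 43 per arm, or 129. The primary F-test power comes to 82.8% (stated 83%).

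**Assumptions not in the plan.** A normal latent threshold, a linear relation with FM-UE change, and the true correlations r used below.

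**1. Will the graded fallback be used?** Fewer than 10% of 129 means 12 or fewer. For a binomial count with n = 129, P(X ≤ 12) = 0.0008 at 20% absence and 0.040 at 15%.

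**2. What the binary form keeps.** The correlation is multiplied by φ(z_q)/√(q(1−q)), where q is the proportion absent. At q = 0.20, z = −0.842 and φ = 0.280, so the factor is 0.280/0.400 = 0.70, and 0.70² = 0.49.

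| Absent | Explained variance kept |
|---|---|
| 10% | 34% |
| 15% | 43% |
| 20% | 49% |
| 25% | 54% |
| 30% | 58% |

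At 20% absent with other latent shapes, the share kept is 48% (uniform), 45% (t with 5 df), and 27% or 61% (lognormal, depending on the direction of skew).

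**3. What an obtainable graded measure keeps.** Orient the scale so that absence is the lower tail, and set absent subjects to the cut point c = −0.842.
- Covariance with the latent scale = 1 − q = 0.80.
- Mean = cq + φ = 0.112.
- Second moment = c²q + (1 − q) + cφ = 0.706.
- Variance = 0.706 − 0.112² = 0.694.
- Correlation = 0.80/√0.694 = 0.96, which keeps 92% of explained variance.

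The binary form therefore keeps 0.490/0.923 = 53% of what ceiling-coded rMT keeps.

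**4. Power for one pooled correlation.** Monte Carlo, 3,000 replicates, n = 110, two-sided 5%, 20% absent:

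| Truth | Test | r = 0.20 | r = 0.25 | r = 0.30 |
|---|---|---|---|---|
| Graded | Binary | 30% | 45% | 61% |
| Graded | Ceiling-coded rMT | 52% | 73% | 87% |
| Graded | Presence + rMT among those with an MEP (2 df) | 43% | 64% | 80% |
| Step | Binary | 56% | 75% | 89% |
| Step | Presence + rMT among those with an MEP (2 df) | 45% | 64% | 82% |

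The two-part test gains 12 to 20 points if the truth is graded and loses 7 to 11 if it is a step. At the 10% level that the plan uses elsewhere (Fisher z, r = 0.30), ceiling-coded rMT against binary is 92% against 71% at n = 110, and 95% against 77% at n = 129.

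**5. Could the trial separate the two markers?** If both truly correlate 0.40 with FM-UE change, the binary TMS term would show about 0.40 × 0.70 = 0.28. A Steiger test of 0.40 against 0.28 at n = 110, assuming a correlation between the markers of 0 to 0.5, gives p of about 0.33 to 0.18.

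**The case against.** The strongest defence is that an absent MEP is not an arbitrary cut. It is a physiological state at the edge of what the stimulator can measure, and section 8.1.2.2 links it to severe corticospinal injury. Section 2.2 (A.7) cites two stimulation studies in which presence itself went with improvement, and a yes/no marker is a natural selection rule. This stands: it justifies keeping presence, and under a pure step the binary form loses nothing. It does not show that thresholds among subjects with an MEP carry no information.

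Second, amplitude is a graded TMS measure planned for the same aims. A reader might infer that the plan discards graded TMS information altogether; the documents do not support that. Amplitude nevertheless fills the gap only partly at baseline. It is recorded at an intensity titrated to about 1 mV, so values are drawn together among subjects who reach that level. Gradation remains mainly among those who have an MEP but cannot reach it. The pre/post comparison of rMT addresses change, not baseline selection.

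Third, a reader might infer that the comparison is tilted against TMS. That follows only if presence is the sole TMS term set against wCST-LL, which the available text does not settle. Nor would equal true strength produce a clear win for imaging: imaging would usually rank first, but step 5 shows the study could not reliably tell the markers apart.

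Finally, the power figures concern one pooled correlation. A treatment-by-biomarker model, which the predictive-biomarker interest in A.7 would call for, was not simulated.

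**Conclusion.** The point holds conditionally, as a low-cost improvement to an exploratory analysis. At the plan's own expected rate the graded index will almost certainly not be used, so rMT will be analysed only as MEP present or absent. If the relation with FM-UE change is graded, the binary form keeps about 49% of explained variance at 20% absent under normality and linearity (27% to 61% for the other shapes checked); the correlation itself falls by 30% under normality.

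The plan supplies neither the shape nor the correlation, so an unconditional statement that half the signal is lost would go too far. Any disadvantage to TMS against wCST-LL extends only as far as MEP presence is the TMS term used. The primary analysis and sample size are not affected.

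**What to change.** In section 8.1.2.2, and in the SAP wherever the biomarker analysis is specified:

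1. Keep MEP presence (1/0) as the simple selection marker and report it alone.
2. Remove the switch at 10% absent.
3. Whatever the percentage absent, always report a graded analysis beside it: either presence plus affected-side rMT among subjects with an MEP, or rMT (or the asymmetry index) with absent set to the ceiling. Name one of these in advance.
4. State which TMS variables, including amplitude, are compared with wCST-LL.

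**Cost.** Wording only, since rMT is already collected on both sides. The two-part form uses one extra degree of freedom in a main-effect model. In a three-arm treatment-by-biomarker model it uses two more interaction terms (four instead of two). If the truth is a pure step, the two-part test gives up about 7 to 11 points of power at the correlations examined; reporting presence alone as well keeps that result visible.

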8.2 ADVERSE EVENTS AND SERIOUS ADVERSE EVENTS

A tDCS questionnaire will be used in each intervention session to assess the common adverse events or tolerability issues associated with its use. Adverse events, including serious adverse events will be collected during the intervention period. Only serious adverse events or clinically related (possibly or definitely) adverse events will be collected after intervention period. Please refer to AE reporting section for details.

8.2.1 DEFINITION OF ADVERSE EVENTS (AE)

An adverse event (AE) is defined as any new untoward medical occurrence or worsening of a preexisting medical condition in a clinical investigation subject administered study intervention and that does not necessarily have a causal relationship with this intervention. An AE can therefore be any unfavorable and unintended sign (such as an abnormal laboratory finding), symptom, or disease temporally associated with the use of the investigational intervention, whether or not considered related to the investigational intervention. Adverse events can be spontaneously reported or elicited during open-ended questioning, examination, or evaluation of a subject.

8.2.2 DEFINITION OF SERIOUS ADVERSE EVENTS (SAE)

A SAE is any untoward medical occurrence that:

- results in death;
- is life-threatening (defined as an event in which the participant was at risk of death at the time of the event; it does not refer to an event which hypothetically might have caused death if it were more severe);
- requires inpatient hospitalization or causes prolongation of existing hospitalization;
- results in persistent or significant disability/incapacity;
- is a congenital anomaly/birth defect;
- is an important medical event (defined as a medical event(s) that may not be immediately life-threatening or result in death or hospitalization but, based upon appropriate medical and scientific judgment, may jeopardize the subject or may require intervention (e.g., medical, surgical) to prevent one of the other serious outcomes listed in the definition above. Examples of such events include, but are not limited to, intensive treatment in an emergency room or at home for allergic bronchospasm; blood dyscrasias or convulsions that do not result in hospitalization.)

The definition of SAE excludes the following hospitalizations:

- A visit to the emergency room or other hospital department < 24 hours, that does not result in admission (unless considered an important medical or life-threatening event);
- Elective surgery, planned prior to signing consent;
- Admissions as per protocol for a planned medical/surgical procedure;
- Routine health assessment requiring admission for baseline/trending of health status (e.g., routine colonoscopy);
- Medical/surgical admission other than to remedy ill health and planned prior to entry into the study (appropriate documentation is required in these cases);
- Admission encountered for another life circumstance that carries no bearing on health status and requires no medical/surgical intervention (e.g., lack of housing, economic inadequacy, caregiver respite, family circumstances, administrative reason).

8.2.3 CLASSIFICATION OF AN ADVERSE EVENT

8.2.3.1 SEVERITY OF EVENT

The severity of AEs will be reported using the grading system outlined in the NCI Common Terminology Criteria for Adverse Events Version 4.03 (CTCAE). The CTCAE provides a grading (severity) scale for each AE term and AEs are listed alphabetically within categories based on anatomy or pathophysiology. The CTCAE displays Grades 1-5 with unique clinical descriptions of severity for each AE based on this general guidance:

The complete definitions of these grades are:

- Grade 1: Mild; asymptomatic or mild symptoms; clinical or diagnostic observations only; intervention not indicated AE.
- Grade 2: Moderate; minimal, local or noninvasive intervention indicated; limiting age-appropriate instrumental activities of daily living (preparing meals, shopping for groceries or clothes, using the telephone, managing money, etc.).
- Grade 3: Severe or medically significant but not immediately life-threatening; hospitalization or prolongation of hospitalization indicated; disabling; limiting self-care activities of daily living (bathing, dressing and undressing, feeding self, using the toilet, taking medications, and not bedridden).

- Grade 4: Life-threatening consequences; urgent intervention indicated.
- Grade 5: Death related to AE.

8.2.3.2 RELATIONSHIP TO STUDY INTERVENTION

All adverse events (AEs) must have their relationship to study intervention assessed by the clinician who examines and evaluates the subject based on temporal relationship and his/her clinical judgment. The degree of certainty about causality will be graded using the categories below. In a clinical trial, the study product must always be suspect.

1. Unrelated: The temporal relationship between treatment exposure and the adverse event is unreasonable or incompatible and/or adverse event is clearly due to extraneous causes (e.g., underlying disease, environment);
2. Unlikely: Must have both of the following 2 conditions, but may have reasonable or only tenuous temporal relationship to intervention:
 - Could readily have been produced by the subject's clinical state, or environmental or other interventions.
 - Does not follow known pattern of response to intervention.
3. Reasonable Possibility: Must have at least 2 of the following 3 conditions:
 - Has a reasonable temporal relationship to intervention.
 - Could not readily have been produced by the subject's clinical state or environmental or other interventions.
 - Follows a known pattern of response to intervention.
4. Definitely: Must have all 3 of the following conditions:
 - Has a reasonable temporal relationship to intervention.
 - Could not possibly have been produced by the subject's clinical state or have been due to environmental or other interventions
 - Follows a known pattern of response to intervention.

8.2.3.3 EXPECTEDNESS

In general, expected adverse reactions are AEs that are known to occur for the study intervention being studied and should be collected in a standard, systematic format using a grading scale based on functional assessment or magnitude of reaction. Identify the source of the reference safety information used to determine the expectedness of the AE (e.g., IB, approved labeling). Expectedness is assessed based on the awareness of AEs previously observed, not on the basis of what might be anticipated from the properties of the study intervention. An AE will be considered unexpected if the nature, severity, or frequency of the event is not consistent with the risk information previously described for the study intervention.

8.2.4 TIME PERIOD AND FREQUENCY FOR EVENT ASSESSMENT AND FOLLOW-UP

The IMSM who is independent of any involvement with the study will monitor the study with regard to the safety concerns when adverse events or serious adverse event occurs. The IMSM will review all SAEs and determine whether they are related to study drug administration (as described above); a query to the site will be generated to amend the AE narrative if necessary for

any questions or clarifications regarding an event. Periodically throughout the study, the Executive Committee and the IMSM will review reports on the incidence rates of all reported AEs, whether serious or not and blinded to treatment assignment. Should such monitoring uncover issues that may threaten subject safety (e.g., unexpectedly high rate of AEs), a notification will be sent to the DSMB liaison for review proposing further actions to be taken, if any. Two statistical reports will be generated semiannually (unless requested at an alternative interval by the IMSM or DSMB) – an open report to be distributed to the Executive Committee and IMSM, and a closed report to be distributed only to the DSMB. Each semi-annual report will provide cumulative summary statistics on enrollment, subject status in the study, baseline characteristics, protocol violations, safety data (including a summary of the most frequent and most serious AEs, and a listing of all subjects who were terminated from the study and the reason for termination), and data management/quality information. The open report statistics will be provided for the overall study with no separation of intervention groups. The closed report will provide cumulative summary statistics by partially blinded intervention group to DSMB members, the NIH liaison, and the project's unblinded statistician. All people with access to the closed reports are fully independent of trial operation and have no impact on subject recruitment, intervention, and assessment. If the DSMB wishes to be completely unblinded for these reports, a sealed identification envelope will be provided to the DSMB liaison; this envelope can be opened at the discretion of the DSMB.

